Study Protocol/Statistical Analysis Plan
Evaluating Technology-Based Fall Prevention Interventions
NCT03190460

9/27/2016

Objectives

The primary study objective is to explore the effectiveness of a 16-week cognitive training (CT) intervention to reduce risk and incidence of fall in community-dwelling older adults at risk for fall. Additional objectives of the study are to explore the effectiveness of a CT intervention on cognition and functional outcomes and to examine the feasibility and acceptability of the study protocol and intervention in this population.

Outcomes

Primary Outcome. At time of allocation, participants will be provided with a Monthly Fall Calendar and instructed in its use. At the end of each day participants are asked to place one of 3 letters in the box for the day: "N" for no fall; "F" for fall; and "I" for fall resulting in an injury), considered the "gold-standard" for falls assessment (See Table 1). For purposes of this study, a fall was defined as an "unintentional". For individuals who experience multiple falls in a single day, they are asked to denote the number (ex. "F-2"). Fall calendars will be collected monthly (See Table 2), and a new calendar provided to the participant during the study period. The time period for primary outcome assessment is falls over the period of 4 months. For any fall resulting in injury, we will request permission from the participant to obtain medical records for any treatment sought at time of injury.

Secondary Outcomes. Of interest as a secondary outcome in this study is reduction in risk of fall at the end of the 16-week intervention (See Tables 1 and 2). This is defined by 1) an increase in the 10M walking speed from baseline or 2) an increase in the Balance test score from baseline.⁴⁰ As secondary endpoints, we will measure cognitive outcomes (using the Cambridge Neurological Assessment Battery [CANTAB]), additional gait and postural sway measures (using body-worn inertial sensor system, the APDM Mobility Lab, Portland, OR; See Tables 1 and 2), and disability (Gill Disability Scale). We will explore if there is retention of benefit of the intervention on fall risk, gait, balance and cognitive outcomes one month following end of the intervention. Feasibility and acceptability of the study protocol and CT intervention will also be evaluated.

Table 1. Summary of Outcome Measures and Source of Measurement

Measure	Source (Instrument/Test[s])
PRIMARY OUTCOME	
Falls and Injurious Falls	Self-Report (Prospective Fall Calendar)
SECONDARY OUTCOMES	
Fall Risk	10M Walk Test 90 Second Balance Test
Cognition Speed of Processing & Response Time Attention Working Memory Task Shifting Planning and Decision Making	CANTAB Simple Response Time Rapid Visual Information Processing Verbal Recognition Memory Spatial Working Memory Intra-Extra Dimensional Set Shift

	Cambridge Gambling Task One Touch Stockings of Cambridge Stop Signal Test
Quantitative Gait and Turning Measures Gait speed (m/s) cadence (steps/min) stride length (m) turn duration (s) turn peak velocity (m/s)	APDM Inertial Sensors Walking trials under testing conditions of: Usual Pace 4-Meter walking laps x 4 Usual Pace 7-Meter walking laps x 2 (if space allows) Fast Pace 4 or 7-Meter walking laps x 2 (space dependent)
Postural Balance Measures: (medial heel-to-medial heel distance = 10 cm) ISway JERK (m^2/s^5) ISway PATH (m^2/s^2) ISway Mean velocity (MV; m/s) ISway Root mean squared (RMS; m/s^2)	APDM Inertial Sensors (ISway): (Inertial sensor at 5 th lumbar level) Static Standing 30-second trials under six conditions: normal base-firm, eye open and eyes closed; narrow base-firm, eye open and eyes closed; normal base, foam surface, eye open and eyes closed
Disability	Gill Disability Scale

Study Design

The design is a two-group randomized controlled trial following a 1-week run-in procedure comparing 16-weeks of a web-based CT intervention to attention control (See Table 2).

Baseline Visit (-T1)

If eligible for inclusion after the in-person screening, the research staff member discusses the project in detail with the individual to ascertain interest in further participation and to allow for provision of informed consent. Following informed consent, the baseline visit commences. At this visit, participants are asked about a) demographics (age, gender, race/ethnicity, formal education, income level, insurance status); b) pre-existing conditions (Charlson method); c) current medications (brown bag method). Questionnaires are administered to participants at baseline to assess: 1) social support (MOS Social Support Survey) and 2) functional status (Gill Disability Scale). Participants undergo an assessment of cognitive abilities using the Cambridge

Table 2. Study Protocol (*denotes data are collected, but is secondary outcome)

	Study period							
		Enrollment	Allocation	Post-allocation				Exit
Time point	-T2	-T1	T0	T1 (4 wks)	T2 (8 wks)	T3 (12 wks)	T4 (16 wks)	T5 (20 wks)

Eligibility screening								
Phone screening	X							
In-person screening		X						
10M walk		X						
90 sec balance								
Informed consent		X						
Run-In Period		X	X					
Vision screen								
Medication review								
Home safety check			X					
Allocation			X					
Intervention								
Active Control				XXXXXXX	XXXXXXX	XXXXXXX	XXXXXXX	
Web-based Cognitive Training				XXXXXXX	XXXXXXX	XXXXXXX	XXXXXXX	
Assessments								
Baseline								
Demographics		X						
Pre-existing conditions		X						
Medications			X					
Social Support			X					
Outcome Variables								
Primary								
Falls/Injurious Falls				X	X	X	X	*
Secondary								
Fall Risk								
10M walk		X			X		X	X
90 sec balance		X			X		X	X
Cognition			X					
CANTAB			X					
Gait/Turning					X		X	X
APDM		X			X		X	X
Postural Sway			X		X		X	X
APDM			X		X		X	X
Disability			X		X		X	X
Gill Disability			X		X		X	X
Other Variables								
Short Physical Performance Battery		X			X		X	X
Timed Up and Go		X			X		X	X
Exit Interview								

Neuropsychological Test Automated Battery (CANTAB) to provide an external method of assessment to that provided by the CT intervention (See Table 1 for specific tests). Lastly, in-home gait and mobility measures are assessed. Gait, mobility and postural sway data are

collected using a body-worn *inertial sensor* system, the APDM Mobility Lab system (APDM Wearable Technologies, Portland, OR). Use of the APDM system involves "instrumenting" the participant with 6 body worn inertial sensors (2 ankle, 2 wrist, 1 waist belt, 1 upper torso) that contain tri-axial accelerometers, gyroscopes, and magnetometers. Participants are asked to wear walking shoes during the assessments. A gait belt and guarding technique⁶¹ is used by a trained investigator during all testing for safety. Data are recorded via wireless transmission from the inertial sensors to a laptop computer and processed with Mobility Lab software. For the instrumented walking assessment, participants are first asked to walk continuous laps with approximately 180-degree turns, at their comfortable (or usual) pace. They complete four 4-meter laps and two 7-meter laps (if space allows) at usual pace. Lastly, participants are asked to walk as quickly as possible, but not so quickly that they lose their balance (2 x 4 or 7-meters; see Table 1 for measures). Participants are able to take rest breaks between activities as needed.

For the postural sway assessment, data are collected with APDM ISway during 6 static standing trials: (1) eyes open/normal base/firm surface (medial heel-to-medial heel distance = 10 cm), (2) eyes open/narrow base/firm surface (feet together) (3) eyes closed/normal base/firm surface, and (4) eyes closed/narrow base/firm surface, (5) eyes open/usual base/foam surface, (6) eyes closed/usual base/foam surface. Participants wear walking shoes and are asked to stand still and keep their arms at their sides during testing. During the eyes open standing conditions, participants are instructed to focus on an "x" placed at eye-level on the wall in front of them. Participants do not use an assistive device, but wear a gait belt and are closely guarded and assisted as needed into the starting position. Measures utilized to assess postural sway are detailed in Table 1. In addition to the gait and balance measures, we collected data to obtain instrumented assessment of mobility: a) the Short Physical Performance Battery (SPPB) and b) the Timed Up and Go (TUG). The SPPB includes tests of static balance, gait speed, and sit to stand. For the sit to stand trial, participants are instructed to move from a seated position to a standing position five times as quickly, but as safely as possible. Participants undertake two trials, with the fastest of the two trials used as the measure.

Run-in and Allocation (T0)

During the 1-week run-in period, a trained member of the research team meets with the study subject three times over the course of a week (approximately 20 minutes per visit) to perform: 1) vision screen; 2) medication review and 3) home fall safety check. This run-in period allows the study staff to provide hazard reduction interventions per CDC recommendations prior to randomization to reduce the risk of these issues introducing bias across groups.

Following successful completion of the run-in period, participants are randomly allocated (1:2) to either a group that is the attention control (**n=20**) or to the group that receives cognitive training (CT) intervention for a total of 16 weeks (**n=40**). Participants are not to be informed that they were assigned to "attention control" or "cognitive training" conditions; rather, individuals in both groups are told that the aim of the study is to determine whether participation in "computer learning activities" reduces the risk of falls and improves functional ability. Sealed envelopes, prepared in advance, assign the participants to one of the two groups. The randomization schedule is prepared by the consulting statistician using block randomization (blocks of 6) prior to the research team's initial visit to interested parties. This approach ensures that consent is obtained prior to disclosure of group assignment and persons consent to participate in the study, regardless of the group they are assigned to. The envelope is not opened until completion of the run-in procedure. The principal investigator, co-investigators and outcome assessors are blinded to allocation until the end of the trial.

Intervention

Cognitive training, also known as "brain training", involves scheduled completion of specific tests of executive function, visuospatial orientation and perceptual speed. The CT is completed using a web-based computer interface (Cognifit, Inc.), with task difficulty tailored to the participant's abilities. We will use the Cognifit research interface as it allows tailoring of the intervention to specific tasks selected by the research team.

The individual completes a 14-task baseline testing session, after which the program identifies individualized, tailored training goals for the intervention tasks. Individualized feedback is provided to the user regarding progress towards goals during each session. Our intervention includes 48 training sessions over 16 weeks (recommended 3 sessions per week; each session lasts approximately 20 minutes and covers 3 different cognitive tasks tailored to individual baseline ability and progress to date). Training sessions can be completed on either PC or Mac platform and use a user identified login/password allowing secure access at the individual's home or a community setting per user accessibility and preference. The training allows the user to pick up from the last session to promote completion of the intervention. Because of their linkage to fall and injury prevention, we selected the following specific cognitive tasks to target in the intervention:

- Reaction Time (the ability to perceive and process a stimulus and respond)
- Processing Speed (the ability to fluently perform easy/over-learned tasks)
- Awareness (the ability to evaluate one's own cognitive functioning, realization, perception or knowledge)
- Divided Attention (the ability to execute more than one task at a time)
- Inhibition (the ability to ignore irrelevant information while performing a task)
- Planning (the ability to anticipate and develop the best way to execute a task)
- Shifting (the ability to redirect attention from one channel of information to another)
- Updating (the ability to respond in a flexible and adaptive manner to keep up with environmental changes)

We track sessions completed on a weekly basis and provide reminders as needed.

Discontinuation of intervention is made on participant request.

Attention Control

Participants assigned to the attention control condition are provided with programmatic activities that are designed to control for nonspecific treatment effects (computer use, interaction with study staff). Participants will engage in an equal number of sessions (3 sessions/week for 16 weeks) watching preselected healthy aging-related video content on the computer (e.g. NIH Senior Health videos on talking with your provider, taking medications safely, and making the most of a medical visit, how to exercise safely). Participants will be asked to briefly note any information gained from each video on a personal discussion board provided to them within the content module. We track sessions completed on a weekly basis and provide reminders as needed. Discontinuation of intervention is made on participant request.

8-, 16- and 20-week Assessments

A member of the research team blinded to intervention/control group assignment conducts participant outcome assessments at the 8-, 16- and 20-week time periods (see Table 2). These assessments occur in same setting and under similar conditions to baseline testing (e.g., same shoes are to be worn). Following the 20-week assessment, an exit interview is

completed in order to gain insight into the protocol's acceptability including participant perceptions of the CT intervention. Participant interviews use a semi-structured interview protocol as a guide to explore their experiences, overall perceived benefits, challenges and attitudes towards the study protocol. All interview sessions are digitally recorded.

ANALYSIS

All planned statistical analyses will be performed using intention-to-treat. The primary time point of interest in this analysis is the 16-week post-randomization outcome assessment; however, means, standard deviations and distributions will be used to describe the outcomes of interest at baseline, midpoint of active intervention phase and 4 weeks post completion of intervention (week 20 post-randomization). A value of $p<0.05$ will be considered statistically significant. Should there be significant differences between groups on baseline demographic variables despite randomization, we will examine the relationship between the variable and the outcome using sensitivity analyses.

The primary outcome of interest in the proposed RCT is reduction number of falls and injurious falls (See Table 1) at the end of the intervention (16 weeks). We are also interested in the retention of effect 1-month post-intervention. Number of falls and injurious falls will be determined from fall calendar data. Between group differences will be assessed using Mann Whitney U test. Of secondary interest as outcome in this study is reduction in risk of fall which is determined by an increase in the 10M walking speed from baseline and an increase in the Balance test score from baseline. Between group differences will be assessed using Student's t-test. In exploratory analyses, we will examine the change in risk of fall over time using linear mixed models for longitudinal data. As secondary endpoints, we will measure cognitive outcomes (CANTAB), functional outcomes (walking Gill Disability, inertial sensor gait and turn measures, and ISway measures; See Table 1). Outcomes will be compared between groups using either t-tests or Mann-Whitney U tests as appropriate. In exploratory analyses, we will examine the change in outcome measures over time using linear mixed models for longitudinal data.

To better understand feasibility of the study, we will estimate the proportion of older adults found eligible for inclusion who actually agree to participate in such a study. Further, we will compare the characteristics of those who are willing to participate with those who are not. We will also evaluate numbers of study who complete the study protocol and note any differences in participant characteristics in those who drop out. We will also note the numbers of older adults who express interest in the study but are not eligible. To evaluate acceptability of the study procedures and intervention, transcripts of interview sessions will be digitally recorded and transcribed verbatim for descriptive content analysis.

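### Reduced fall risk is defined with *or* in the Outcomes section and with *and* in the Analysis section, and nothing reconciles the two

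*Combined protocol and SAP*

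**What the plan says.** Fall risk is the first secondary outcome, and lowering the risk of falling is also part of the primary objective. The combined protocol and SAP defines a reduction twice:

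- Outcomes, Secondary Outcomes: "defined by 1) an increase in the 10M walking speed from baseline or 2) an increase in the Balance test score from baseline".
- Analysis, paragraph on outcomes: "determined by an increase in the 10M walking speed from baseline and an increase in the Balance test score from baseline".

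Table 1 lists the two tests under Fall Risk with no connector ("10M Walk Test 90 Second Balance Test"). Table 2 gives each test its own row (the second is "90 sec balance") and schedules both at -T1, week 8, week 16 and week 20.

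On analysis, the plan says "Between group differences will be assessed using Student's t-test". It adds, as exploratory work, that "we will examine the change in risk of fall over time using linear mixed models for longitudinal data". On timing, "The primary time point of interest in this analysis is the 16-week post-randomization outcome assessment"; the rest of that sentence plans descriptive summaries at baseline, the midpoint and week 20. The only decision criterion is that p<0.05 "will be considered statistically significant". No multiplicity rule is given, and sidedness is not stated.

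**The concern.** The two sentences describe one named outcome and differ in the word that decides what counts as success. The Outcomes sentence is worded as a definition with numbered alternatives, so its *or* is hard to dismiss as loose phrasing.

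If the two measures agree, the wording makes no difference. If walking speed favours CT and balance does not, or the reverse, one section supports a statement that fall risk fell and the other does not. The plan would then allow either summary to be chosen once the results are known. This bears on the risk half of the primary objective, although the outcome itself is secondary and the trial is exploratory.

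**Working it through.** **1. The texts side by side.** The plan gives no power, SD, effect size or sample-size figure for fall risk, so there is no stated figure to reproduce.

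| Place | Connector | Rule for combining |
|---|---|---|
| Outcomes, Secondary Outcomes | *or* | either measure |
| Analysis, outcomes paragraph | *and* | both measures, or a plain list of two |
| Table 1, Fall Risk | none | none |
| Table 2, Fall Risk | none, separate rows | none |

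**2. What the connector applies to.** Each definition speaks of an increase from baseline; neither mentions significance or a comparison between arms. Two readings are open: each participant is classed as improved or not, or the results of two between-arm comparisons are combined. A t-test and linear mixed models suit continuous measures better than a yes/no classification, and the tables list the tests separately. The group-level reading is therefore the more likely one, but it is not stated. Step 3 depends on it.

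**3. Size on the group-level reading (illustration).**

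Inputs from the plan: 40 CT and 20 control (Run-in and Allocation) and p<0.05 (Analysis).

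Assumptions: two-sided tests, no dropout, pooled t-tests on changes with SD 1, the same true effect of 0.7 SD on both measures, and correlation r between the two changes of 0 to 0.7.

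- Degrees of freedom: 40 + 20 − 2 = 58; critical value 2.0017.
- Standard error: √(1/20 + 1/40) = 0.2739. Noncentrality: 0.7/0.2739 = 2.556.
- Power for one measure (noncentral t): 71.0%.
- By hand at r = 0: both = 0.710² = 50%; at least one = 1 − 0.290² = 92%; exactly one = 2 × 0.710 × 0.290 = 41%.

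By simulation for the other correlations, counting only results that favour CT:

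| r | *or* met | *and* met | Wordings disagree |
|---|---|---|---|
| 0 | 92% | 50% | 41% |
| 0.3 | 88% | 54% | 34% |
| 0.5 | 85% | 57% | 28% |
| 0.7 | 82% | 60% | 22% |

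Disagreement is *or* minus *and*, taken before rounding.

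With no true effect, *or* is met in favour of CT in 4.9% to 4.2% of trials and *and* in 0.06% to 0.8% (r = 0 to 0.7).

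**4. Sensitivity to the assumed effect.** With a normal approximation and the same range of r:

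- 0.5 SD on both measures: disagreement runs from 69.4% − 19.9% = 49.5% down to 57.2% − 32.1% = 25.1%.
- 0.8 SD on both measures: from 97.2% − 69.2% = 28.0% down to 91.0% − 75.4% = 15.6%.

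**5. Operating characteristics of two possible rules** (0.7 SD on both, r = 0 to 0.7).

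- Both measures at p<0.05: power 50% to 60%.
- Either measure with Holm adjustment (the smaller p must be below 0.025): power 84% to 73%; chance of a false claim favouring CT with no true effect 2.5% to 2.2%.

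**6. Baseline adjustment.** Let ρ be the correlation between baseline and week 16, with equal SDs σ at the two visits. The variance of a change is 2σ²(1 − ρ); the residual variance after adjustment for baseline is σ²(1 − ρ²). The ratio of CI widths is √((1 + ρ)/2): 0.866 at an assumed ρ = 0.5 and 0.949 at 0.8.

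**The case against.** The strongest reply is that the *and* in the Analysis section may simply list two continuous measures, each given its own t-test. The same two tests would then be run under either wording, and only a summary sentence about a secondary outcome would be in doubt. Both measures are named in advance in both tables, so quietly dropping one would be visible. This has weight: the planned tests are not in dispute, and a t-test suits such measures. It does not remove the conflict, because the Outcomes section still defines reduced risk by either measure and nothing says how a split result is to be described.

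The percentages also rest on an effect size and a correlation that the plan does not give. That stands, and they serve only as an illustration. The Outcomes definition also carries a citation that cannot be consulted here and that may bear on the intended rule.

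A reader might infer more than the documents support in two ways:

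- **That the plan contains an either/both rule at p<0.05 between arms.** It does not. The connector may apply to each participant, and the calculation above adopts the group-level reading.
- **That the question of retained benefit one month after the intervention lacks a claim rule.** The plan only explores retention. It describes outcomes at week 20 and models change over time in exploratory analyses, and it names no week-20 significance test for fall risk. No claim rule is clearly missing there.

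**Conclusion.** The plan is wrong as written on this point: two current passages define the same outcome differently and no other text settles it. That much is certain from the documents.

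The consequence is conditional. On the group-level reading, the two wordings give different conclusions in 41% to 22% of trials under an assumed 0.7 SD effect on both measures and correlation 0 to 0.7. The figure moves with the assumed effect. The participant-level reading is not excluded and was not sized.

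The finding does not show that the t-test is unsuitable, and it does not touch the primary analysis of falls. A reader might also conclude that requiring both measures at p<0.05 is the correct repair. The documents do not support that: the choice trades power against false claims and belongs to the sponsor. Adjusting each comparison for baseline is a separate improvement, not a consequence of the *or*/*and* conflict.

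**What to change.** Use the same text in the Outcomes and Analysis sections:

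> *Fall risk is assessed by two separate continuous secondary outcomes at week 16, 10M walking speed and 90-second balance score. Each is compared between arms by a mean difference adjusted for its -T1 value, with 95% CI, and both results are always reported.*

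This settles the level at which the outcome is read and needs no combined claim. If the sponsor wants a single statement that fall risk was reduced, one rule should be written into both sections before unblinding: both measures at p<0.05, or either measure with Holm adjustment. Step 5 of the working gives the power of each.

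Keep week 20 descriptive and exploratory, on the same two measures and with no claim rule.

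**Cost.** No new data are needed, because Table 2 already schedules both tests at -T1 and week 16. The change is more than wording, since the adjusted comparison replaces the unadjusted t-test named in the plan and should be recorded as a change of method. In return, each CI is about 87% to 95% as wide as with change scores, for an assumed baseline-to-week-16 correlation of 0.5 to 0.8. If the sponsor prefers to keep the t-test, the conflict is still resolved by the rest of the text.

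### The single published block size of 6 at 1:2 lets up to 28.9% of assignments be known before the envelope is opened, for anyone who knows the earlier ones in the block

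*Combined protocol and SAP*

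**What the plan says.** All of the allocation text is in the section Run-in and Allocation (T0).

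- **Ratio and size.** After the run-in, "participants are randomly allocated (1:2) to either a group that is the attention control" (n=20) or to the group that receives the "cognitive training (CT) intervention for a total of 16 weeks (n=40").
- **List.** The consulting statistician prepares the schedule "using block randomization (blocks of 6"). One size is given. No variation in size and no stratification is described.
- **Concealment.** "Sealed envelopes, prepared in advance, assign the participants to one of the two groups". Timing is also protected: "The envelope is not opened until completion of the run-in procedure". The text does not say who holds or opens the envelopes, or whether they are opaque or numbered in sequence.
- **Entry step.** Allocation takes place "Following successful completion of the run-in period". Before it, "a trained member of the research team meets with the study subject three times over the course of a week" for a vision screen, a medication review and a home safety check. What counts as success is not stated.
- **Blinding.** "The principal investigator, co-investigators and outcome assessors are blinded to allocation until the end of the trial". The section on the 8-, 16- and 20-week assessments repeats this for assessors. Run-in staff and staff who follow session completion are not mentioned either way.

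**The concern.** Opening the envelope late stops anyone reading the next assignment early. It does not stop anyone inferring it. With a fixed block of known size and composition, earlier assignments narrow down the remaining ones, and the end of each block becomes certain while the envelope is still sealed.

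Session tracking and reminders differ in content by arm (training tasks or videos), so staff doing that work could learn assignments. The plan does not say whether the same people do run-in visits, or whether run-in staff are kept from earlier assignments.

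Consent comes before the run-in, and completing the run-in is the last step before allocation. A person who foresees the arm could, even without intent, affect whether or when a participant passes that step. The result would be selection before randomisation. Intention-to-treat analysis starts at randomisation and cannot remove it. The primary comparison of falls is an unadjusted Mann-Whitney U test. The only planned check for imbalance, in the Analysis section, is triggered by significant differences in baseline demographic variables, so a difference in frailty could escape it. With 20 controls, a few shifted entries could matter. The size of any resulting bias cannot be worked out from the documents; only predictability can.

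**Working it through.** **Inputs, all from Run-in and Allocation (T0).** Block size 6; ratio 1:2; arms of 20 and 40.

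**Arm sizes.** 60/6 = 10 blocks. 10 × 2 = 20 control and 10 × 4 = 40 CT, which agrees with the plan. The plan states no predictability figure to reproduce.

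**Certain assignments, all earlier ones in the block known.** There are C(6,2) = 15 equally likely orders. Place k is certain when all places from k to 6 belong to one arm. The number of such orders is C(k−1,2) for CT, plus 1 order at k = 5 and 5 orders at k = 6 for control.

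| Place | Certain CT | Certain control | Probability certain |
|---|---|---|---|
| 1 | 0 | 0 | 0 |
| 2 | 0 | 0 | 0 |
| 3 | 1 | 0 | 1/15 |
| 4 | 3 | 0 | 3/15 |
| 5 | 6 | 1 | 7/15 |
| 6 | 10 | 5 | 15/15 |

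Sum: (1 + 3 + 7 + 15)/15 = 26/15 = 1.733 per block. 1.733/6 = 28.9%, or 17.3 of 60. By arm: 20/15 = 1.33 CT and 6/15 = 0.40 control per block.

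**Best-guess accuracy.** The chance of a correct best guess is 10/15 at each of places 1 to 3, 11/15 at places 4 and 5, and 15/15 at place 6. (30 + 22 + 15)/15 = 67/15, and 67/15 divided by 6 = 74.4%. Always guessing CT gives 4/6 = 66.7%.

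**If earlier envelopes are still unopened.** Run-ins last a week and may overlap. With one earlier envelope unopened, place k is certain only if every place from k−1 on belongs to one arm, so the table shifts by one place: (1 + 3 + 7)/15 = 11/15, and 11/15 divided by 6 = 12.2% (about 7 of 60). With two unopened: (1 + 3)/15 = 4/15, and 4/15 divided by 6 = 4.4% (about 3 of 60). The documents give no recruitment pace, so 4.4% to 28.9% is a range under assumption.

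**Varying block sizes (illustration; the sizes are an assumption).** Blocks of 3, 6 and 9 in random order were simulated against an observer who knows the three sizes and all earlier assignments, but not which size is in use.

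| | Fixed 6 | 3/6/9, total ignored | 3/6/9, total of 60 used |
|---|---|---|---|
| Certain | 28.9% | about 4% | about 6% |
| At least 90% confident | 28.9% | about 14% | about 16% |
| At least 80% confident | 34.4% | about 39% | about 39% |
| Best-guess accuracy | 74.4% | about 74% | about 74% |

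Under the fixed block, the highest probability below certainty is 4/5 (place 2 after a control), so the 90% row equals the certain row. That case has probability 5/15, which gives the 80% row: (26 + 5)/15 divided by 6 = 34.4%.

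A larger fixed block does less than mixing sizes: 21.4% are certain with a fixed block of 9 and 17.0% with a fixed block of 12.

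**The case against.** The strongest reply is that the plan already protects allocation. Consent and run-in come before opening, the list comes from a statistician, and the investigators and outcome assessors are blinded. Silence about other staff is not evidence that they know anything. The trial is small and describes its aim as exploratory, and fixed blocks are a common choice.

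Much of this stands. Someone might infer that 29% of assignments will be foreseen. The documents do not support that: the figure needs one person who knows the block size, where the block starts and every earlier assignment in it, with each envelope opened before the next entry decision. Someone might also infer that passing the run-in is a staff judgement. The text only leaves the criterion undefined; it may mean no more than that the three tasks were done. Nor do the documents show that run-in staff are unblinded, or that entry is steered.

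Most of the certainty also concerns the arm already expected. CT has probability 2/3 without any knowledge, and certain control is 0.40 of 6 places, or 6.7% (about 4 of 60). Full knowledge raises guess accuracy by 74.4 − 66.7 = 7.7 points.

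The remedy has limits too. Mixed sizes do not reduce predictions held with at least 80% confidence, and overall accuracy hardly moves. Keeping run-in staff from knowledge of earlier assignments would address the mechanism more directly.

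What does not stand is that late opening answers the point. It prevents disclosure of the next envelope, not inference from the earlier ones.

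**Conclusion.** The point holds as an avoidable opportunity, not as a demonstrated bias. The plan publishes one block size and does not say that staff who do run-in visits, open envelopes or track sessions are blinded to earlier assignments. At most 28.9% of assignments (about 17 of 60) can be certain in advance. That bound rests on full knowledge of the block. It falls to 12.2% or 4.4% when one or two earlier envelopes are unopened, and lower still if run-in staff never learn assignments. The documents give neither the recruitment pace nor the holder of the envelopes, so the figure that applies in practice cannot be fixed.

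Because the bias itself is unquantified and the trial is exploratory, this is an improvement to consider and not a defect that invalidates the design. It earns a place because the change removes most certain foreknowledge at almost no cost.

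**What to change.** Have the consulting statistician prepare the list with randomly varying block sizes that are multiples of 3 (for example 3, 6 and 9), so that 1:2 is kept within each block. Replace the stated size in Run-in and Allocation (T0) with a sentence saying that sizes vary and are withheld, and keep the sizes out of the protocol and all staff documents until the trial ends. The same edit could say who holds and opens the envelopes, whether run-in staff are kept from earlier assignments, and what completing the run-in means.

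The gain should be described as removing certain knowledge, not as making allocation unpredictable.

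Cost: one new list and a short protocol edit, with no added participants or visits. The downside is slightly looser balance if recruitment stops inside a block of 9.
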